6.2.2 Non-Amgen Investigational Product: Daratumumab

6.2.2.1 Daratumumab: Dosage, Administration, and Schedule

Daratumumab will be administered as an IV infusion. On days when more than 1 investigational products are administered, the required administration is as follows: dexamethasone, other pre-infusion medications for daratumumab, carfilzomib, daratumumab, and post-infusion medications for daratumumab.

- On days 1 and 2 of cycle 1, daratumumab will be administered at 8 mg/kg in 500 mL normal saline each day.
 - If the subject's first 2 infusions of 8 mg/kg daratumumab are well-tolerated (defined as an absence of infusion-related reaction [IRR] > grade 1), the first infusion of 16 mg/kg in 500 mL normal saline will be given once weekly as a

single infusion for the remaining doses of the first 2 cycles, ie, days 8, 15, and 22 of cycle 1; and days 1, 8, 15, and 22 of cycle 2, then every 2 weeks for 4 cycles (cycles 3 to 6), and then every 4 weeks for the remaining cycles or until disease progression.

- If the 8 mg/kg infusions are not well-tolerated (defined as IRR > grade 1), the dilution will be in 1000 mL of normal saline until the subject completes an infusion without > grade 1 IRR. For any infusions that would require a large volume (eg, 1000 mL); the daratumumab dose may be divided in 2 days.

The administration may be within \pm 2 days for each scheduled dose. See [Table 13](#) to review the arm 1 dosing schedule.

Each subject's dose will be calculated based on the subject's weight rounded to the nearest kilogram. Dosing calculations do not need to be changed for weight changes that are < 10% from baseline. The pharmacist will calculate the required volume and number of vials needed. The daratumumab infusion rates are provided in [Table 5](#) and [Table 6](#).

The planned dose (mg/kg), dose (mg), start date/time, stop date/time, reason for change in planned dose, reason for dose change/withheld, reason for dose delay, reason for dose interruption and package lot number of daratumumab is to be recorded on each subject's eCRF.

Table 5. Daratumumab Infusion Rate

C1D1 and C1D2 (8 mg/kg)		C1D8 (16 mg/kg)		Subsequent Infusions	
Time (minutes)	mL/hr	Time (minutes)	mL/hr	Time (minutes)	mL/hr
0 – 60	50	0 – 60	50 ^a	0 - 60	100 ^b
61 – 120	100	61 – 120	100	61 - 120	150
121 – 180	150	121 - 180	150	121 - 180	200
181 – 240	200	181 - 240	200	181-	200
500 mL		500 mL ^a		500 mL	

CxDx = cycle X day X; IRR = infusion-related reaction.

^a If the subject's first 2 infusions of 8 mg/kg daratumumab are well-tolerated (defined as an absence of IRR > grade 1), the first infusion of 16 mg/kg daratumumab will be administered at an initial rate of 50 mL/hour and increased by 50-mL/hour increments at 60-minute intervals, as tolerated, to a maximum rate of 200 mL/hour. If the 8 mg/kg infusions are not well-tolerated (defined as IRR > grade 1), the dose may be split in 2 days (on 500 mL each day).

^b Modified rates should only be used if at least 1 16 mg/kg infusions of daratumumab was well-tolerated as defined by an absence of >grade 1 infusion-related reactions during a final infusion rate of \geq 100 mL/hr.

The duration of infusion may be shortened starting in cycle 2 onwards to a 90-minute infusion for subjects without a history of an infusion related reaction after the third dose of daratumumab.

The 90-minute daratumumab accelerated infusions (Barr et al, 2017) can be administered at an initial rate of 20% of the total dose over 30 minutes, followed by the remaining 80% of the total dose over 60 minutes (90-minute total infusion time).

- Rapid infusion will be given in a total volume of 500 mL
- This allows for a rate of 200 mL/hour for the first 30 minutes and a rate of 400 mL/hour for the final 60 minutes.
- If a subject experiences any grade infusion related reaction, the subject will not be eligible to receive additional rapid infusions until he/she has received standard infusion daratumumab without any grade hypersensitivity reaction.

Table 6. Accelerated/Shortened Infusion Rate

Accelerated/Shortened Infusion	Dilution Volume	Initial Infusion Rate (first 30 minutes)	Subsequent Infusion Rate (last 60 minutes)	Maximum Infusion Rate
	500 mL	200 mL/hour	400 mL/hour	400 mL/hour

Rapid infusion will be given in a total volume of 500 mL. This allows for a rate of 200 mL/hour or the first 30 minutes and a rate of 400 mL/hour for the final 60 minutes. If a subject experiences any grade infusion related reaction, he/she is not eligible to receive additional rapid infusions until they have received standard infusion daratumumab without any grade hypersensitivity reaction.

Source: Barr et al, 2017.

See Section 7.3.10 for details on vital sign monitoring during daratumumab and other infusions.

6.2.2.1.1 Pre-infusion Medications for Daratumumab

On daratumumab infusion days, subjects will receive the following medications 1 to 3 hours before daratumumab infusion (and prior to carfilzomib infusion):

1. paracetamol 650 to 1000 mg orally (PO) or IV, and
2. antihistamine (diphenhydramine 25 to 50 mg or equivalent, PO or IV), and
3. leukotriene inhibitor (montelukast 10 mg PO or equivalent) should be given.

Dexamethasone is also required pre-infusion, as well as 1 day after daratumumab infusion. Refer to Section 6.3.1 for additional information on dexamethasone dosing.

6.2.2.1.2 Post-infusion Medications for Daratumumab

Any post-infusion medication will be administered after the infusion has completed.

For the prevention of delayed IRR, all subjects will receive long- or intermediate-acting corticosteroid (see Section 6.2.2.1.1).

In the absence of infusion-related adverse events after the first 3 infusions, post-infusion corticosteroids should be administered per investigator discretion.

For subjects with a higher risk of respiratory complications (eg, subjects with mild asthma or subjects with COPD who have an FEV1 < 80% at screening or developed FEV1 < 80% during the study without any medical history) the following post-infusion medications must be administered:

- antihistamine (diphenhydramine or equivalent)
- leukotriene inhibitor (montelukast or equivalent)
- short-acting β 2 adrenergic receptor agonist such as salbutamol aerosol
- control medications for lung disease (eg, inhaled corticosteroids \pm long-acting β 2 adrenergic receptor agonists for subjects with asthma; long-acting bronchodilators such as tiotropium or salmeterol \pm inhaled corticosteroids for subjects with COPD)

In addition, these at-risk subjects may be hospitalized for monitoring for up to 2 nights after an infusion. If subjects are hospitalized, then their spirometry test (FEV1) should be performed and documented before discharge. If these subjects are not hospitalized, then a follow-up telephone call should be made to monitor their condition within 48 hours after all infusions. If the subject has not experienced a significant medical event but is hospitalized overnight only for observation, the hospitalization should not be reported as a serious adverse event. Investigators may prescribe bronchodilators, H1-antihistamines, and corticosteroids that are deemed necessary to provide adequate supportive care in the event a bronchospasm occurs after subjects are released from the hospital/clinic. If an at-risk subject experiences no major IRRs, then these post-infusion medications may be waived after 4 doses at the investigator's discretion.

Any post-infusion medication will be administered after the infusion has completed.

6.2.2.2 Daratumumab: Dosage Adjustments, Delays, Rules for Withholding or Restarting, Permanent Discontinuation

Individual dose modification of daratumumab is not permitted, but dose delay is the primary method for managing daratumumab-related toxicities.

During a cycle, a daratumumab dose must be held if any of the following criteria below are met, to allow for recovery from toxicity. The criteria for a dose delay are:

- grade 4 hematologic toxicity, except for grade 4 lymphopenia
- grade 3 thrombocytopenia with bleeding
- febrile neutropenia
- neutropenia with infection, of any grade
- grade 3 or higher non-hematologic toxicities with the following exceptions:
 - grade 3 nausea that responds to antiemetic treatment within 7 days
 - grade 3 vomiting that responds to antiemetic treatment within 7 days
 - grade 3 diarrhea that responds to antidiarrheal treatment within 7 days
 - grade 3 fatigue that was present at baseline or that lasts for < 7 days after the last administration of daratumumab
 - grade 3 asthenia that was present at baseline or that lasts for < 7 days after the last administration of daratumumab

Administration of daratumumab may be restarted upon recovery from toxicity to grade 2 or baseline, with the exception that grade 2 laryngeal edema or grade 2 bronchospasm must be fully recovered.

If daratumumab administration does not commence within the prespecified window (Table 7) of the scheduled administration date, then the dose will be considered a missed dose. Administration may resume at the next planned dosing date. A missed dose will not be made up.

Table 7. Daratumumab Administration Schedule

Cycles	Frequency	Dose Held	Dosing Re-start
1 and 2	Weekly (q1wk)	> 3 days	next planned weekly dosing date
3 to 6	Biweekly (q2wks)	> 7 days	next planned biweekly dosing date
7+	Every 4 weeks (q4wks)	> 14 days	next planned every 4 weeks dosing date

Doses of daratumumab may be delayed up to 4 weeks (cycles 1 to 6) or up to 8 weeks (cycle 7 and beyond). If day 1 of a cycle is delayed, day 1 of subsequent cycles should be adjusted accordingly to maintain the 28-day cycle duration. However, if a within-cycle dose is delayed, then the dates of the subsequent within-cycle doses should not be adjusted. Any adverse event deemed to be related to daratumumab that requires a dose hold of more than 4 weeks (cycles 1 to 6) or more than 8 weeks (cycle 7 and beyond) will result in permanent discontinuation of daratumumab. If a dose delay occurs, then PK and PDn assessments should be performed on the actual administration day of daratumumab, not on the original scheduled administration day.

Daratumumab can be discontinued in the event of a treatment-related toxicity that, in the opinion of the investigator, warrants discontinuation. The subject will be considered on protocol treatment while receiving either carfilzomib or daratumumab (ie, if either carfilzomib or daratumumab are discontinued or interrupted, the subject is still considered on treatment if still taking the other investigational product).

For subjects who are diagnosed with HBV reactivation while on daratumumab treatment, study treatment should be interrupted until the infection is adequately controlled (See Section 6.7.1).

6.2.2.3 Daratumumab: Management of Infusion-related Reactions

Subjects should be carefully observed during daratumumab infusions. Trained study staff at the clinic should be prepared to intervene in case of any infusion reactions occurring, and resources necessary for resuscitation (eg, agents such as epinephrine and aerosolized bronchodilator, also medical equipment such as oxygen tanks, tracheostomy equipment, and a defibrillator) must be available at the bedside. Attention to staffing should be considered when multiple subjects will be dosed at the same time.

If an IRR develops, then the infusion should be temporarily interrupted. Subjects who experience adverse events during the infusion must be treated according to the investigator's judgment and best clinical practice. Subjects should be treated with acetaminophen, antihistamine, or corticosteroids, as needed. Intravenous saline may be indicated. For bronchospasm, urticaria, or dyspnea, subjects may require antihistamines, oxygen, corticosteroids, or bronchodilators. For hypotension, subjects may require vasopressors. In the event of a life-threatening IRR (which may include pulmonary or cardiac events) or anaphylactic reaction, daratumumab should be discontinued and no additional daratumumab should be administered to the subject.

Infusion-related Reactions of Grade 1 or Grade 2

If the investigator assesses a grade 1 to 2 IRR adverse event to be related to administration of study drug, then the daratumumab administration should be paused. When the subject's condition is stable, daratumumab administration may be restarted at the investigator's discretion.

If the subject experiences a grade 2 or higher event of laryngeal edema, or a grade 2 or higher event of bronchospasm that does not respond to systemic therapy and does not resolve within 6 hours from onset, then the subject must be withdrawn from daratumumab treatment.

Infusion-related Reactions of Grade 3 or Higher

For IRR adverse events (other than laryngeal edema or bronchospasm) that are grade 3, the daratumumab administration must be stopped and the subject must be observed carefully until resolution of the adverse event or until the intensity of the event decreases to grade 1, at which point the daratumumab administration may be restarted at the investigator's discretion. If the intensity of the adverse event returns to grade 3 after restart of the daratumumab administration, then the subject must be withdrawn from daratumumab treatment.

For IRR adverse events that are grade 4, the daratumumab administration must be stopped and the subject withdrawn from daratumumab treatment.

Recurrent Infusion-related Reactions

If a grade 3 IRR (or grade 2 or higher event of laryngeal edema, or a grade 2 or higher event of bronchospasm) recurs during or within 24 hours after a subsequent daratumumab administration, the daratumumab treatment must be discontinued.

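### As punctuated, Protocol 6.2.2.3 withdraws daratumumab after any grade 2 or higher laryngeal edema, while 6.2.2.2 and the recurrence rule in 6.2.2.3 both foresee further dosing after such an event

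*Protocol*

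**What the plan says.** Three rules in the protocol bear on giving daratumumab again after laryngeal edema.

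- **Withdrawal rule** (6.2.2.3, under the sub-heading for grade 1 or grade 2 infusion-related reactions). The preceding paragraph says that once the subject's "condition is stable, daratumumab administration may be restarted" at the investigator's discretion. The rule then begins "If the subject experiences a grade 2 or higher event of laryngeal edema, or a grade 2 or higher event of bronchospasm that". It continues with two joint conditions, failure to respond to systemic therapy and persistence past 6 hours from onset, and concludes that the subject must come off daratumumab.
- **Restart rule** (6.2.2.2, after the list of hold criteria). The general condition is "Administration of daratumumab may be restarted upon recovery from toxicity to grade 2 or baseline". Two airway events are then held to a stricter standard: "with the exception that grade 2 laryngeal edema or grade 2 bronchospasm must be fully recovered". No 6-hour limit appears here, and withdrawal is not mentioned for these events.
- **Recurrence rule** (6.2.2.3, under recurrent infusion-related reactions). Daratumumab must be discontinued if a grade 3 reaction, or grade 2 or higher laryngeal edema or bronchospasm, recurs at a later infusion or in the 24 hours after it.

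On infusion reactions, neither 6.2.2.2 nor 6.2.2.3 refers to the other or says which prevails.

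**The concern.** The withdrawal rule names laryngeal edema, then a comma, then bronchospasm with its own repeated grade wording, and only then the two conditions. Read in the ordinary way, the conditions restrict bronchospasm alone, and laryngeal edema of grade 2 or higher is an unconditional reason for withdrawal. On that reading the laryngeal edema parts of the restart rule and of the recurrence rule have nothing left to govern.

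At stake is a mandatory safety rule for an airway event. The outcomes on offer are opposite: re-exposure once recovered, or loss of the rest of the daratumumab course. Protocol 3.2 plans about 120 sites, so the rule has to be read the same way by many investigators. Inconsistent application would also make daratumumab exposure in the KdD arm depend partly on how a site parses a sentence.

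**Working it through.** No sample size, power, event count or alpha enters this point, so there is nothing to calculate. The check is to take one event, grade 2 or higher laryngeal edema during a daratumumab infusion (leaving aside grade 4, for which 6.2.2.3 has a separate withdrawal rule), and follow the three rules under each reading of the two conditions.

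| Course of the event | Conditions attach to bronchospasm only | Conditions attach to both events |
|---|---|---|
| Responds to systemic therapy, or resolves within 6 hours | Withdrawal rule: withdraw. Restart rule: restart possible after full recovery. **Conflict.** | Withdrawal rule not triggered. Restart rule: restart possible after full recovery. Consistent. |
| Neither responds nor resolves within 6 hours, later recovers fully | Withdrawal rule: withdraw. Restart rule: restart possible. **Conflict.** | Withdrawal rule: withdraw. Restart rule, taken alone, would permit restart. Settled if the mandatory rule prevails over the permissive one. |
| Comes back at a later infusion | Cannot arise, because the first event ended treatment. **Recurrence rule is empty for laryngeal edema.** | Recurrence rule: discontinue. Consistent. |

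Two further checks:

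1. *Could the restart rule refer only to residual edema?* The non-hematologic hold criterion in 6.2.2.2 starts at grade 3, so the clause might mean that a higher-grade event which has come down to grade 2 is not yet recovered enough. Even so, it foresees restart after an event that was at least grade 2. Under the bronchospasm-only reading, 6.2.2.3 would already have ended treatment.
2. *Could the sections apply at different times?* One might say that 6.2.2.3 governs the interrupted infusion and 6.2.2.2 the next scheduled dose. That does not help here, because withdrawal from daratumumab treatment also rules out the next dose. Nor can it reconcile the withdrawal and recurrence rules, which stand in the same section.

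The bronchospasm-only reading therefore clashes with two other rules. The joint reading removes the clash in the first and third rows and leaves only a question of precedence in the second.

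**The case against.** The strongest reply is that the sentence can be read the other way. Both the restart rule and the recurrence rule put laryngeal edema and bronchospasm side by side and treat them alike, which suggests that the two conditions were meant for both. The rules then form a sequence: withdraw if the event neither responds nor resolves, require full recovery before restart if it does, and discontinue if it recurs. That is a plausible account of intent, and it is why this is a defect of wording and not of design. But the reader has to infer it from other paragraphs, against the punctuation of the sentence that contains the mandatory rule.

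A second reply is that a permission to restart never overrides a duty to withdraw, so an investigator who withdraws breaks no rule. That stands for edema that fails both conditions under the joint reading. Under the bronchospasm-only reading it avoids the conflict only by leaving the laryngeal edema clause of 6.2.2.2 without effect.

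A reader might also infer a second contradiction, for grade 3 infusion reactions. Section 6.2.2.2 holds doses for "grade 3 or higher non-hematologic toxicities with the following exceptions", does not list infusion reactions among the exceptions, and says dosing "may be restarted upon recovery from toxicity to grade 2 or baseline". Section 6.2.2.3 requires observation until resolution or "until the intensity of the event decreases to grade 1, at which point the daratumumab administration may be restarted". The documents do not support calling this a contradiction. The second is a specific rule for an infusion that has been stopped. The first is a general, permissive rule for held doses. Waiting for grade 1 satisfies both. Neither withdraws a subject after a first grade 3 reaction other than laryngeal edema or bronchospasm; withdrawal follows only if grade 3 returns on restart or recurs later.

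**Conclusion.** The point holds for laryngeal edema. As written, the withdrawal rule in 6.2.2.3 conflicts with the restart rule in 6.2.2.2 and with the recurrence rule in its own section, unless the response and 6-hour conditions are read onto both events, which the sentence does not say. The conclusion rests on the ordinary reading of the punctuation. If the sponsor intended the joint reading, the rules largely fit together and only the wording needs repair.

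For an affected subject the readings differ by the whole remaining daratumumab course. How many subjects that is cannot be derived, because the documents give no rate for grade 2 or higher laryngeal edema; it is probably small. A reader might reach for the approximate 50% first-infusion reaction rate in Protocol 2.4.1. That figure comes from pooled earlier daratumumab trials, is not limited to these events or grades, and is said to fall to about 10% at the second infusion and to be rare afterwards. It does not size this problem.

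Nor should the point be stretched to the efficacy result. The full analysis set analyses subjects as randomized, so alpha, sample size and the primary PFS analysis are unaffected. That sites would in fact act differently is an inference from the text and is not documented. The consequence is confined to consistent patient management and to daratumumab exposure in the KdD arm. It should still be corrected, because the rule is mandatory, concerns an airway event, and costs very little to clarify.

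**What to change.** Reconcile the withdrawal and recurrence rules in 6.2.2.3 with the restart rule in 6.2.2.2:

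1. Reword the withdrawal sentence so that it states whether the response and 6-hour conditions apply to laryngeal edema as well as to bronchospasm, for example by listing the two events separately, each with its own conditions.
2. Add a cross-reference in 6.2.2.2 saying which section governs infusion-related reactions, and check that the laryngeal edema clauses of the restart and recurrence rules still have cases to apply to.

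Which clinical rule should stand is for the sponsor and its clinical and safety advisers; no view is offered here. The cost is about two sentences of protocol text and a notice to sites, with no new data and no change to the SAP.

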6.3 Non-Amgen Non-investigational Product: Dexamethasone

6.3.1 Dexamethasone: Dosage, Administration, and Schedule

Dexamethasone, a non-Amgen non-investigational product, will also be used in this study. On days when more than 1 investigational product is administered, the required order of administration is as follows: dexamethasone, pre-infusion medications for daratumumab, carfilzomib, daratumumab, and post-infusion medications for daratumumab.

Dexamethasone 40 mg will be taken orally or by IV infusion weekly. Dexamethasone must be given intravenously on cycle 1 days 1 and 2. See [Table 13](#) and [Table 14](#) to review the arm 1 and arm 2, dosing schedules, respectively. Dexamethasone IV or PO will be given on successive days, at 20 mg each treatment day on weeks with carfilzomib and/or daratumumab infusions. All subjects, regardless of age, will be required to receive 20 mg of dexamethasone on days 1 and 2 of cycle 1 (as a preinfusion medication for daratumumab infusion) followed by 20 mg of methylprednisolone or equivalent on the third day (see [Appendix N](#) for corticosteroid dose equivalents).

For days when dexamethasone is given in the absence of other IV infusion (neither carfilzomib nor daratumumab is scheduled), it may be given within ± 2 days for each

scheduled dose. Dexamethasone will be administered at least 30 minutes (but no more than 4 hours) prior to carfilzomib and within 1 to 3 hours from the daratumumab dose.

Additional details regarding dexamethasone is provided in the Investigational Product Information Manual.

6.3.2 Dexamethasone: Dosage Adjustments, Delays, Rules for Withholding or Restarting, Permanent Discontinuation

All dexamethasone administrations must be within the 2 days of the scheduled administration; however, it must be given on days carfilzomib and/or daratumumab will be administered.

The dose, date, and time are to be recorded on each subject's eCRF. The reason for dose change of dexamethasone is also to be recorded on each subject's eCRF.

For conditions that do not require dexamethasone dose reduction, refer to Section 6.4.

For subjects > 75 years of age or subjects whose weekly dexamethasone dose has been reduced to 20 mg/week, 20 mg of dexamethasone will be given as a preinfusion medication for daratumumab infusion, followed by 8 mg of dexamethasone prior to carfilzomib infusion on days 9 and 16 of cycle 1. Starting with cycle 2, 20 mg dexamethasone must be given on days daratumumab is administered (without 8 mg dose on subsequent carfilzomib dosing day), otherwise the 20-mg dose can be split across carfilzomib dosing days (eg, 12/8, 10/10, etc, as shown in Table 13 and Table 14).

When carfilzomib is permanently discontinued, investigators may at their discretion omit dexamethasone on days when given in the absence of daratumumab based on their assessment of the subject's steroid tolerance.

Subjects in arm 1 on cycles 7+ without previous IRR, may decrease or omit dexamethasone premedication, if the subject cannot tolerate 20 mg of dexamethasone or equivalent.

